14.3. Analysis Populations

There are two pre-defined analysis populations in this study.

- Safety Population: All participants treated with study treatment (either a partial dosing or a complete dosing) will be included in the Safety Population. All safety analyses (e.g., adverse events, clinical laboratory) will be performed using the Safety Population.
- Intent-to-Treat Population: The Intent-to-Treat (ITT) population will be defined as all Safety Population infantile-onset participants from Stage 2 who have received the full dose of study medication. All efficacy analyses will be performed using the ITT population. This is the primary population of interest for efficacy assessments.

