14.2. General Methods

Stage 1 includes 12 participants at differing doses of AXO-AAV-GM2 which precludes tabulation of outcomes in a mathematically reasonable manner. Thus, the analysis of Stage 1 outcomes will focus comparisons of individual participant data using graphical displays (e.g., line-scatterplots of each participant's outcomes over time) to allow for visual inspection of any trends between participants. Limited tabulations may be created to present overall Stage 1 data (e.g., as for adverse event incidence), as the data warrant. The methods provided below are generally intended to describe the analysis of Stage 2 outcomes but may also apply to Stage 1 in some instances (e.g., adverse event coding).

Stage 2 will include a comprehensive assessment of both efficacy and safety outcomes, with tables, listings, and figures generated. Data will be tabulated and presented using both descriptive and inferential statistics (where applicable) where specified. Select continuous endpoints will be assessed a mixed model for repeated measures (MMRM) of changes over time with effects for visit, the baseline value (of the outcome of interest), and a random effect for participant. Graphical displays of least squares mean (LSMean) changes over time will be presented.

The statistical analysis will be undertaken by the Sponsor or a third-party vendor. The statistical analysis and report will conform to the relevant ICH requirements.

SAS version 9.4 or later will be used for the analysis.

There is no formal hypothesis being tested. However, comparison to external data sources (e.g., literature, NH studies) may be performed as the data allow.

Confidential Page 83 of 97

Version 8.0, 09 June 2023

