14.4. Primary Efficacy Endpoints

The Primary Efficacy Endpoints are:

- Clinical Function: BSID-III Gross Motor domain
 - The continuous clinical outcome BSID-III Gross Motor domain will be assessed as a change from baseline to Week 48 (Month 12).
- Surrogate Biologic Marker: CSF HexA activity
 - CSF HexA activity will be assessed as a change from baseline to Week 48 (Month 12), including the baseline (pre-treatment) value as a covariate in the model.

This is an open-label, single-arm study in which outcomes will be compared to a pre-specified external (e.g., NHS) study database or to the literature. There is no alpha-control applied for having co-primary endpoints as no formal hypothesis testing is planned.

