Head control	Unable to maintain upright	Wobbles	All the time upright			
Rolling	No rolling	Rolling to side	Prone to supine	Supine to prone		
Sitting	Cannot sit	Sits with support at hips	Props	Stable sit	Pivots (rotates)	
Crawling	Does not lift head	On elbow	On outstretched hand	Crawling flat on abdomen	On hands and knees	
Standing	Does not support weight	Supports weight	Stands with support	Stands unaided		
Walking	No walking	Bouncing	Cruising (holding on)	Walking independently		

The HINE-2 contains a standardized tool for assessing motor milestone achievement, consisting of structured, developmentally appropriate items that assess incremental changes in head control, sitting, voluntary grasp, ability to grasp, ability to kick, rolling, crawling, standing, and walking (Bishop et al. 2018). Bishop and colleagues reported the first use of the HINE-2 in a prospective nusinersen treatment trial with SMA infants and demonstrated that motor milestone assessment using the HINE-2 was feasible and practical in symptomatic, fragile (extremely low functioning at

Confidential Page 85 of 97

Clinical Study Protocol: AXO-GM2-001

Version 8.0, 09 June 2023

baseline) infants with type 1 SMA. A natural history study using the HINE-2 indicated that SMA infants do not achieve motor milestones and seldom make even incremental improvements with development, as also reported for a significant proportion of individuals with infantile-onset TSD or SD. (De Sanctis et al. 2016)

For the HINE-2 category of ability to kick, similar to the definition of improvement in (i) above, worsening is defined as at least a 2-point decrease or decrease to the lowest possible score of no kicking. For the other 6 categories, worsening is defined as at least a 1-point decrease. Participants who die or withdrew from the study will be counted as non-responders and will be included in the denominator for the calculation of the percentage.

• Proportion of infantile-onset participants maintaining the ability to sit without support as assessed in HINE-2 at Week 4, Week 12, Week 24 and Week 48.

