Of the subset of infantile-onset participants enrolled with the ability to sit up – the proportion maintaining the ability to sit without support through Week 48 will be provided. A Kaplan-Meier plot of time to event (time to loss of ability to sit upright) will be provided to allow for visual inspection of the time-profile of the loss. For participants who discontinue the study prior to Week 48, every effort will be made to determine sitting ability at Week 48.

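### The Intent-to-Treat set in Section 14.3 admits only fully dosed Stage 2 children, so a partially dosed child drops out of every efficacy analysis

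*Combined protocol and SAP*

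**What the plan says.** Section 14.3 (Analysis Populations) states: "There are two pre-defined analysis populations in this study".

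- **Safety Population**, the wider of the two: "All participants treated with study treatment (either a partial dosing or a complete dosing) will be included in the Safety Population".
- **Intent-to-Treat (ITT) population**, the narrower: "all Safety Population infantile-onset participants from Stage 2 who have received the full dose of study medication". The section names it as the main population for efficacy and adds: "All efficacy analyses will be performed using the ITT population".

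No all-treated, modified ITT or per-protocol efficacy set is named, and no sensitivity analysis on a different set.

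Other sections that bear on the point:

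- Section 8.1 gives the treatment as two procedures on two consecutive days: thalamic infusion on Day 1 and intracisternal/intrathecal infusion on Day 2.
- Section 8.6 rules out dose adjustment once the Stage 2 dose is chosen. It does not say how much of the planned dose must be delivered to count as full.
- Section 14.4 says that "outcomes will be compared to a pre-specified external (e.g., NHS) study database or to the literature".
- Section 14.5 has a rule for the HINE-2 responder endpoint: "Participants who die or withdrew from the study will be counted as non-responders and will be included in the denominator".
- Section 14.2 describes the Stage 2 output as "with tables, listings, and figures generated", so a partially dosed child may still appear in individual listings.

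**The concern.** An intent-to-treat set should not depend on what happens once treatment is under way. This one does: a child enters it only if both procedures deliver the full dose. An infusion may be cut short because of an early complication, so completing the dose can be related to how the child is doing.

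Stage 2 has no concurrent control, and its estimates are meant to be read against natural history data. Natural history children are not selected on completing a procedure; the treated children would be. Section 8.3.1 defends the uncontrolled design partly on the ground that the choice of participants does not affect the results, and this definition weakens that argument.

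There is also a knock-on effect on the HINE-2 rule. A partially dosed child who then dies or withdraws is already outside the efficacy set, so the conservative non-responder rule never reaches that child. This follows from the definition; it is not a contradiction between sections.

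Finally, because full dose has no stated tolerance, membership in a borderline case could be settled after outcomes are known in an open-label study.

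**Working it through.** **Step 1. Set the definitions side by side (Section 14.3).**

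| Stage 2 infantile-onset child | Safety Population | ITT set | Any efficacy analysis |
|---|---|---|---|
| Full dose delivered | Yes | Yes | Yes |
| Administration started, not completed | Yes | No | No |
| Withdrawn before Day 1 (Section 8.2) | No | No | No |

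The second row is the gap.

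**Step 2. Is partial dosing foreseeable?** The Safety Population wording allows for it. Section 8.3.4.1 and the Table 10 footnote let the neurosurgeon stop an infusion for an adverse event or a CT finding. That text is written for Stage 1. The documents give no rate, so the rates below are assumptions. With 10 children (the Stage 2 maximum), the chance of at least one partial dosing is 1 − (1 − p)^10:

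| Assumed p | Chance of at least one in 10 |
|---|---|
| 2% | 18.3% |
| 5% | 40.1% |
| 10% | 65.1% |
| 20% | 89.3% |

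**Step 3. Effect on the HINE-2 responder proportion.** Let n be the number treated and r the number of responders. The all-treated estimate is r/n. Leaving out one non-responder gives r/(n − 1); leaving out one responder gives (r − 1)/(n − 1). All values of r, and n = 6, are assumptions.

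| n | r | All treated | Non-responder left out | Responder left out |
|---|---|---|---|---|
| 10 | 2 | 20.0% | 2/9 = 22.2% | 1/9 = 11.1% |
| 10 | 5 | 50.0% | 5/9 = 55.6% | 4/9 = 44.4% |
| 10 | 8 | 80.0% | 8/9 = 88.9% | 7/9 = 77.8% |
| 6 | 3 | 50.0% | 3/5 = 60.0% | 2/5 = 40.0% |

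For scale, the exact (Clopper-Pearson) 95% interval for 5/10 is 18.7% to 81.3%.

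**Step 4. Effect on the sitting endpoint.** Section 14.5 restricts it: "Of the subset of infantile-onset participants enrolled with the ability to sit up". The denominator may therefore be smaller, and one exclusion weighs more. With assumed subset sizes:

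- 4/8 = 50% becomes 4/7 = 57.1% or 3/7 = 42.9%.
- 3/5 = 60% becomes 3/4 = 75% or 2/4 = 50%.

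**Step 5. Effect on the primary endpoints.** The documents give no standard deviation or expected change for BSID-III Gross Motor or CSF HexA, so no figure in their own units is possible. For a simple mean, let x be the excluded child's change and m the mean of the other n − 1 children. The all-treated mean is [(n − 1)m + x]/n, so exclusion shifts the mean by m − [(n − 1)m + x]/n = (m − x)/n. That is 10% of the gap between the child and the others at n = 10, and 16.7% at n = 6. The planned mixed model for repeated measures, or an adjustment for baseline, would change these weights.

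**The case against.** **The effect is conditional.** If no Stage 2 child is partially dosed, the two sets are identical, and the explicit text on stopping an infusion belongs to Stage 1. This stands as a limit on size. It does not excuse the rule, because Section 14.3 itself provides for partial dosing.

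**A full-dose set is a defensible choice.** Stage 2 is meant to study one selected dose, a partially dosed child received something else, and there is no randomization to protect and no hypothesis test. There is something in this: effect at the full dose is a legitimate question. It supports keeping that set under an accurate name. It does not support making it the only efficacy set or calling it ITT.

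**The external comparison is not firm.** Section 14.2 says only that it may be done if the data allow. Section 14.4, however, says outcomes will be compared, and selection on completed dosing affects the single-arm estimates in any case.

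**The selection is not on outcome.** Completing the dose is settled on Days 1 and 2, before any post-dosing efficacy measurement. That is correct. The concern is selection on an event after treatment starts that may be related to prognosis.

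**Stage 2 analyses are still to be developed in the SAP, and delivery details sit in the Surgical Manual.** A tolerance for full dose may exist there. But Section 14.3 presents its sets as already defined, so deferral does not answer the point.

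**Conclusion.** The concern holds. As written, Section 14.3 puts the wrong label on its efficacy set and excludes any partially dosed Stage 2 child from every efficacy analysis. It should be corrected before Stage 2 outcomes are seen.

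The size can be shown only under assumptions. One exclusion among 10 shifts a HINE-2 proportion by 2.2 to 8.9 percentage points in the cases shown, and the assumed 3/5 sitting subset by 10 to 15 points. The shift can go either way and, for 5/10, is small beside sampling error. A wide interval does not make the denominator right. The HINE-2 consequence is narrow, because it affects only a partially dosed child who also dies or withdraws. Safety reporting is not affected.

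**What to change.** In Section 14.3, replace the ITT definition with wording such as:

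> *All-Treated (Full Analysis) Set: all Stage 2 infantile-onset participants in whom any administration of AXO-AAV-GM2 was started, whatever amount was delivered.*

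- Use this set for all primary and secondary efficacy analyses, with the Section 14.5 non-responder rule applied within it. The wording names no visit, because the Stage 2 administration regimen is still to be identified (Section 7.1.2).
- Do not call it ITT. Children withdrawn before Day 1 under Section 8.2 are not in it; report their number in the disposition table.
- Keep full-dose recipients as a labelled sensitivity set, and fix the tolerance for full dose in the SAP before Stage 2 outcomes are seen.
- Report the number of partially dosed children and the reason for each.

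**Cost:** a few sentences in Section 14.3 and the SAP. No new data are needed, because Sections 8.1 and 8.1.3 already follow every participant. Partially dosed children may dilute the estimate, which the sensitivity set would show.

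**Limit:** Table 15 places the first post-dosing BSID-III at Week 4 and the first post-dosing CSF HexA at Week 12, and neither is done at Week 48 if that visit is by tele-health. A child lost before those weeks adds no change value to the primary endpoints under either set, and a child seen remotely at Week 48 has no Week 48 value.

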14.4. Primary Efficacy Endpoints

The Primary Efficacy Endpoints are:

- Clinical Function: BSID-III Gross Motor domain
 - The continuous clinical outcome BSID-III Gross Motor domain will be assessed as a change from baseline to Week 48 (Month 12).
- Surrogate Biologic Marker: CSF HexA activity
 - CSF HexA activity will be assessed as a change from baseline to Week 48 (Month 12), including the baseline (pre-treatment) value as a covariate in the model.

This is an open-label, single-arm study in which outcomes will be compared to a pre-specified external (e.g., NHS) study database or to the literature. There is no alpha-control applied for having co-primary endpoints as no formal hypothesis testing is planned.

14.5. Secondary Efficacy Endpoints

Secondary efficacy endpoints include both biologic markers of disease and measurements of clinical function.

For the biologic markers (e.g., CSF HexA at later time points, GM2 ganglioside levels), changes from baseline over time will be presented.

For clinical endpoints, outcomes are measured at multiple time points during the course of the 12-month period, and thus will be presented as follows:

Continuous clinical outcomes will be assessed as for the biologic markers, i.e., with changes from baseline over time.

 BSID-III Composite score change from baseline to Week 4, Week 12, Week 24 and Week 48

The proportion of participants will be assessed via time-to-event methods, presented via Kaplan-Meier plots. Comparisons to the NHS study will be made, where possible, using similar methodology as for the primary clinical endpoint.

Confidential Page 84 of 97

- Proportion of Motor Milestone responders based on HINE Section 2 (HINE-2) as assessed in HINE Section 2 at Week 4, Week 12, Week 24 and Week 48
- Responder defined as:
 - i. The participant demonstrated at least a 2-point increase in the motor milestones category of ability to kick or achievement of maximal score on that category (touching toes), or a 1-point increase in the motor milestones of head control, rolling, sitting, crawling, standing, or walking

AND

ii. Among the 7 motor milestone categories (with the exclusion of voluntary grasp), the participant demonstrated improvement (as defined in [i]) in more categories than worsening

Motor milestones are important as they provide a contextualized assessment that is relatable to everyday function and capabilities (Gaussen 1985). The HINE was originally developed to assess development of global neurological function in normal infants (Dubowitz et al. 2005, Haataja et al. 1999) and has been evaluated in several infant populations (Frisone et al. 2002, Romeo et al. 2016, Ricci et al. 2006).

HINE is comprised of eight tests: head control, sitting, voluntary grasp, ability to kick in supine position, rolling, crawling, standing, and walking. There are 26 possible motor milestones that can be achieved using this schema.

MOTOR FUNCTION	MILESTONE PROGRESSION SCORE					
	0	1	2	3	4	
Voluntary grasp	No grasp	Uses whole hand	Index finger and thumb but immature grasp	Pincer grasp		
Ability to kick (in supine position)	No kicking	Kicks horizontal; legs do not lift	Upward (vertical)	Touches leg	Touches toes	
Head control	Unable to maintain upright	Wobbles	All the time upright			
Rolling	No rolling	Rolling to side	Prone to supine	Supine to prone		
Sitting	Cannot sit	Sits with support at hips	Props	Stable sit	Pivots (rotates)	
Crawling	Does not lift head	On elbow	On outstretched hand	Crawling flat on abdomen	On hands and knees	
Standing	Does not support weight	Supports weight	Stands with support	Stands unaided		
Walking	No walking	Bouncing	Cruising (holding on)	Walking independently		

The HINE-2 contains a standardized tool for assessing motor milestone achievement, consisting of structured, developmentally appropriate items that assess incremental changes in head control, sitting, voluntary grasp, ability to grasp, ability to kick, rolling, crawling, standing, and walking (Bishop et al. 2018). Bishop and colleagues reported the first use of the HINE-2 in a prospective nusinersen treatment trial with SMA infants and demonstrated that motor milestone assessment using the HINE-2 was feasible and practical in symptomatic, fragile (extremely low functioning at

Confidential Page 85 of 97

Clinical Study Protocol: AXO-GM2-001

Version 8.0, 09 June 2023

baseline) infants with type 1 SMA. A natural history study using the HINE-2 indicated that SMA infants do not achieve motor milestones and seldom make even incremental improvements with development, as also reported for a significant proportion of individuals with infantile-onset TSD or SD. (De Sanctis et al. 2016)

For the HINE-2 category of ability to kick, similar to the definition of improvement in (i) above, worsening is defined as at least a 2-point decrease or decrease to the lowest possible score of no kicking. For the other 6 categories, worsening is defined as at least a 1-point decrease. Participants who die or withdrew from the study will be counted as non-responders and will be included in the denominator for the calculation of the percentage.

• Proportion of infantile-onset participants maintaining the ability to sit without support as assessed in HINE-2 at Week 4, Week 12, Week 24 and Week 48.

Of the subset of infantile-onset participants enrolled with the ability to sit up – the proportion maintaining the ability to sit without support through Week 48 will be provided. A Kaplan-Meier plot of time to event (time to loss of ability to sit upright) will be provided to allow for visual inspection of the time-profile of the loss. For participants who discontinue the study prior to Week 48, every effort will be made to determine sitting ability at Week 48.

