Biologic and clinical efficacy endpoint measures will be performed for juvenile-onset participants enrolled in Stage 1 of the study. These endpoints will be analyzed in a descriptive manner, separately from that of the infantile-onset participants.

Stage 2

Stage 2 Primary Endpoint(s):

- Clinical Function: BSID-III Gross Motor domain change from baseline to Week 48 (12 months)
- Surrogate Biologic Marker: CSF HexA activity change from baseline to Visit 9/Week 48

Stage 2 Secondary Endpoints(s):

- Changes in Biomarkers:
 - Serum HexA activity levels change from baseline to Week 48 (12 months)
 - CSF GM2 ganglioside levels change from baseline to Week 48 (12 months)
- Biodistribution: Serum and CSF vector DNA levels will be measured over 48 weeks (12 months) to assess the pharmacokinetics of AXO-AAV-GM2
- Clinical Function:
 - BSID-III Composite score change from baseline over Week 48
 - Proportion of Motor Milestone responders based on Hammersmith Infant Neurological Examination (HINE) Section 2 from baseline to Week 48

Responder defined as:

i. The participant demonstrated at least a 2-point increase in the motor milestones category of ability to kick or achievement of maximal score on that category

Confidential Page 14 of 97

Clinical Study Protocol: AXO-GM2-001

Version 8.0, 09 June 2023

(touching toes), or a 1-point increase in the motor milestones of head control, rolling, sitting, crawling, standing, or walking

AND

- ii. Among the 7 motor milestone categories (with the exclusion of voluntary grasp), the participant demonstrated improvement (as defined in [i]) in more categories than worsening
- Proportion of infantile-onset participants maintaining the ability to sit without support as assessed in HINE Section 2 at Week 48

Stage 2 Exploratory Endpoint(s):

- Changes from baseline in developmental age-appropriate clinical function assessments as measured by BSID-III, HINE-2 (Motor), CGI, Neurologic exam, and Vineland-3
- Biomarker changes from baseline over 5 years in:
 - Serum HEXA activity level
 - CSF HEXA activity level
 - GM2 ganglioside in CSF
- Change from baseline in brainstem auditory evoked response (BAER) and visual evoked responses (VER) from baseline to Week 12, Week 24, and Week 48
- MRI brain volume and Diffusion Tensor Imaging (DTI) indices of myelination and brain water change from baseline to Week 12 and Week 48
- MRS indices of metabolite accumulation change from baseline to Week 12 and Week 48

Long-term Follow-up

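### Section 14.5 gives the HINE-2 responder endpoint two incompatible estimators, and the Kaplan-Meier one, if reported, can only equal or exceed the plan's own Week 48 percentage

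*Combined protocol and SAP*

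**What the plan says.** Section 14.5 (Secondary Efficacy Endpoints) introduces the proportion endpoints with one sentence on method: "The proportion of participants will be assessed via time-to-event methods, presented via Kaplan-Meier plots". It adds that natural-history comparisons will be made where possible. The first endpoint listed beneath is the HINE-2 responder proportion, to be assessed at each of four visits (Weeks 4, 12, 24 and 48). The Synopsis describes the same endpoint as "Proportion of Motor Milestone responders based on Hammersmith Infant Neurological Examination (HINE) Section 2 from baseline to Week 48".

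A responder needs a qualifying gain in at least one milestone category and must also satisfy a net condition: "the participant demonstrated improvement (as defined in [i]) in more categories than worsening". Nothing requires the gain to be confirmed or to last.

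Further on, Section 14.5 gives the rule for the percentage: "Participants who die or withdrew from the study will be counted as non-responders and will be included in the denominator".

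The only Kaplan-Meier event the section defines belongs to the other proportion endpoint, maintenance of sitting: "A Kaplan-Meier plot of time to event (time to loss of ability to sit upright) will be provided to allow for visual inspection". No event, confirmation rule or censoring rule is given for a HINE-2 Kaplan-Meier analysis, and the handling of death in the sitting curve is not stated.

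**The concern.** A percentage at a visit and a Kaplan-Meier estimate of time to first response answer different questions when the state can be lost. The percentage asks who is a responder now, out of everyone. The Kaplan-Meier estimate asks who has ever been one, among those still observable.

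The documents themselves describe skills that are gained and then lost. Section 8.3.1 speaks of early milestones followed by regression over a short time, and Section 5 reports that most early motor gains were gone by age 2 years. A child could therefore meet the responder definition at Week 12 and fail it at Week 48.

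No test depends on this endpoint, so what is at stake is the reported rate and its comparison with natural history. In an open-label, single-arm study of up to 10 children, one child is worth 10 percentage points. An ever-responded figure set against a fixed-time external rate would favour treatment through method alone. Leaving both estimators open also lets the choice be made after the data are seen.

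**Working it through.** The plan states no responder rate, death rate or dropout rate for this endpoint, so there is no figure to reproduce. The check asks how the two estimators relate and how far apart they could be.

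**Ordering.** Let N be the children analysed, E the number who meet the definition at any visit, and R the number who meet it at Week 48 and are still in the study. Every child in R is also in E, so R/N ≤ E/N. A Kaplan-Meier estimate that censors deaths and withdrawals shares a censored child's weight among those still at risk, so it is at least E/N. Hence Kaplan-Meier ≥ E/N ≥ R/N. All three agree when no response is lost and nobody dies or withdraws.

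**Worked cases, N = 10 (assumed patterns).** T transient responders are first seen at Week 12 and have lost the response by Week 48. S = 2 sustained responders are first seen at Week 24. D children die between Weeks 12 and 24 without response. The rest are followed to Week 48 and never respond.

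Kaplan-Meier = 1 − (1 − T/10) × (1 − S/(10 − T − D)); ever-responder = (T + S)/10; plan's Week 48 percentage = S/10.

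| T | S | D | Kaplan-Meier | Ever | Week 48 |
|---|---|---|---|---|---|
| 0 | 2 | 0 | 1 − 8/10 = 20% | 20% | 20% |
| 0 | 2 | 2 | 1 − 6/8 = 25% | 20% | 20% |
| 1 | 2 | 1 | 1 − (9/10)(6/8) = 32.5% | 30% | 20% |
| 3 | 2 | 0 | 1 − (7/10)(5/7) = 50% | 50% | 20% |
| 3 | 2 | 2 | 1 − (7/10)(3/5) = 58% | 50% | 20% |

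The ever-responder column shows that counting deaths as failures would not by itself reconcile the methods. Transient gains would still be counted.

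**A simple reversible model (assumed rates).** Let g be the chance of gaining response in each of the four visit intervals and l the chance of losing it. Cumulative first response is 1 − (1 − g)^4. The proportion in response follows p(next) = p(1 − l) + (1 − p)g, starting from 0.

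- g = 0.1, l = 0.3: cumulative 1 − 0.9^4 = 34.4%. In response: 10%, 16%, 19.6%, then 0.196 × 0.7 + 0.804 × 0.1 = 21.8% at Week 48. The gap is about 13 points.
- g = 0.1, l = 0.5, 10% death or withdrawal: in response at Week 48 is 16.2%, times 0.9 = 14.6%, against 34.4%.
- g = 0.1, l = 0: with 10% or 20% dropout the plan's percentage is 0.9 × 34.4% = 31.0% or 0.8 × 34.4% = 27.5%. Censoring alone opens about 3 to 7 points.

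A simulation of the same model with N = 10 gave matching means: 34.5% vs 21.9%, 34.4% vs 14.6%, 34.3% vs 30.9% and 34.5% vs 27.6%. In these scenarios most of the gap comes from transient gains, not deaths.

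**How many deaths to expect.** If the Stage 1 infantile age limit of 20 months (Section 9.1) carries over to Stage 2, the oldest child is about 20 + 48 × 7/30.44 = 31.0 months at Week 48. The prospective natural-history study in Section 5 reports ages at death from 33.08 months. The survival analysis in Section 4, with half alive beyond 3 years, leaves room for some earlier deaths.

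**The case against.** The strongest reply is that the percentage already in Section 14.5 has neither problem. It is visit-wise, and deaths and withdrawals are failures in it. The Kaplan-Meier sentence introduces two endpoints, and the only event defined is loss of sitting, so the author may have meant the curve for sitting alone. The endpoint is secondary, and Section 14.2 says no formal hypothesis is tested.

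Much of this stands. A reader might infer that the plan censors HINE-2 deaths, takes the first gain as the event, and therefore overstates the responder rate. The text says none of these things. Censoring and the first-gain event come from standard practice, and overstatement arises only if the Kaplan-Meier figure is the one reported.

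A reader might also infer that untreated children would often respond by chance at some visit. The documents point the other way. Section 14.1 places the study at ages when decline is expected, and Section 5 gives mean ages of 6.8 months for gaining sitting and 13.1 months for losing it. Section 14.5 notes that a significant proportion of untreated infants seldom improve even incrementally. The net-improvement condition makes chance response harder still in a declining child. Reversibility is documented; frequent new gains without treatment are not.

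What the reply does not remove is the conflict. The Kaplan-Meier sentence, as placed, covers HINE-2 response, and in the standard form it cannot reproduce the plan's own non-responder rule.

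**Conclusion.** The point holds as a conflict between two estimators for one endpoint. If a standard Kaplan-Meier analysis of time to first response were reported as the responder rate or compared with natural history, it would equal or exceed the Week 48 percentage. The documents do not determine by how much. The gap is zero with no transient gains and no dropout, and 12.5 points (32.5% vs 20%) in the moderate case of one transient responder and one death among 10. The larger gaps above rest on assumed gain, loss and dropout rates and illustrate direction, not expected size.

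The sitting curve needs only a statement on death. Counting death as loss is one defensible choice among several, and the plan does not say that such children are censored. The primary endpoints are unaffected.

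**What to change.** In Section 14.5 and the SAP:

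- Remove the HINE-2 responder endpoint from the Kaplan-Meier sentence.
- Define its analysis as the proportion of the ITT population meeting both responder criteria at Week 48, with deaths and withdrawals as non-responders and an exact 95% confidence interval.
- Show the same proportion at Weeks 4, 12 and 24.
- Keep Kaplan-Meier only for time to loss of sitting, and state in advance how death is handled.

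The same edit could close a related gap. Under the footnotes to Table 15, HINE-2 is not done if the Week 48 visit is by tele-health, and the non-responder rule covers only death and withdrawal. The text should say how a child who is in the study but not examined is counted.

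The cost is wording, with no new data collection. The downside is that the reported responder rate may be lower than a Kaplan-Meier figure would have been.

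### The HINE-2 responder rule does not say that the maximal kicking score must be an increase from baseline; applied literally, it makes some children with no net gain responders

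*Combined protocol and SAP*

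**What the plan says.** The proportion of HINE-2 motor milestone responders is a Stage 2 secondary endpoint. The synopsis frames it from baseline to Week 48; Section 14.5 lists Weeks 4, 12, 24 and 48. A responder must meet two conditions.

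- **Condition (i), kicking.** There are two routes: "at least a 2-point increase in the motor milestones category of ability to kick", or "achievement of maximal score on that category (touching toes". In Section 14.5 the second route sits in the clause "ability to kick or achievement of maximal score on that category (touching toes), or a 1-point increase in the motor milestones". The synopsis has the same pair: "at least a 2-point increase in the motor milestones category of ability to kick or achievement of maximal score on that category".
- **Condition (i), the other six categories.** Improvement is "a 1-point increase in the motor milestones of head control, rolling, sitting, crawling, standing, or walking".
- **Condition (ii).** Over seven categories, leaving out voluntary grasp, "the participant demonstrated improvement (as defined in [i]) in more categories than worsening".

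Later in Section 14.5, worsening on kicking is introduced as analogous to improvement: "worsening is defined as at least a 2-point decrease or decrease to the lowest possible score of no kicking". For the other six categories, worsening is a fall of one point or more. Children who die or withdraw stay in the denominator as non-responders.

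Neither place says how to score a child who already touches toes at baseline.

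**The concern.** The first kicking route, and the rule for every other category, state a change. The maximal-score route states only where the child ends. Condition (ii) takes its meaning of improvement from condition (i), so it inherits the gap.

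A programmer who codes the sentence as written will count an unchanged top score as one improved category. The endpoint would then report some children as having gained a motor milestone when they made no net gain. The introduction does name stabilised function as a hoped-for result, but stability is not what this endpoint is named to measure.

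The effect runs one way: the literal reading can add responders and can never remove one. Stage 2 is open-label and single-arm (Section 10.4), and Section 14.5 plans comparison with the natural history study where possible. An unresolved scoring choice of this kind is best settled before results are seen.

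**Working it through.** **Inputs.** Category maxima come from the HINE-2 table in Section 14.5. The improvement and worsening rules are those set out above. Stage 2 size is up to 10 (Section 8.4). No response rate, power or baseline HINE-2 distribution is given.

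**Check of the scale.** Summing the maxima in the order grasp, kick, head, rolling, sitting, crawling, standing, walking: 3 + 4 + 2 + 3 + 4 + 4 + 3 + 3 = 26. This matches the plan's figure of 26 and confirms that 4, touching toes, is the kicking maximum.

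**Step 1: which kicking scores depend on the reading.** There are 5 × 5 = 25 baseline/follow-up pairs. On the literal reading, kicking improves if the rise is at least 2 or the follow-up score is 4. On the change reading, it improves if the rise is at least 2, or the follow-up score is 4 and above baseline. Only the pair 4→4 is classified differently. The pair 3→4 is an improvement on both.

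**Step 2: responder status for a 4→4 child.** Let *a* be the number of the other six categories that improved and *b* the number that worsened.

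- Literal reading: kicking counts as one improvement, so the child responds if 1 + *a* > *b*, that is, *a* ≥ *b*.
- Change reading: the child responds if *a* > *b*.

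The readings differ exactly when *a* = *b*. With six categories, that means (0,0), (1,1), (2,2) or (3,3).

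| Other categories improved, worsened | Literal | Change |
|---|---|---|
| 0, 0 | 1 > 0, responder | 0 > 0 fails, non-responder |
| 1, 1 | 2 > 1, responder | 1 > 1 fails, non-responder |
| 0, 1 | 1 > 1 fails, non-responder | 0 > 1 fails, non-responder |
| 1, 0 | 2 > 0, responder | 1 > 0, responder |

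**Step 3: size.** Each affected child adds 1/N to the proportion. At N = 10 this is 10 percentage points; at any smaller N it is more. As an assumed range only, 0, 1, 2 or 3 affected children out of 10 add 0, 10, 20 or 30 points on the literal reading and nothing on the change reading.

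**The case against.** The strongest reply is that the plan, read as a whole, already means an increase. Achieving a score suggests reaching it, condition (ii) calls the result improvement, the synopsis frames the endpoint from baseline, and the worsening rule is presented as parallel and requires a fall to the bottom score. This is persuasive about intent. A reader might infer that the plan deliberately sets asymmetric rules, or that every unchanged toe-toucher is settled as a responder. The documents do not support either inference: the text calls the two rules alike, and a 4→4 child with a net loss elsewhere fails on both readings. What survives is that the operative clause lacks the words its mirror rule has.

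A second reply is that the case may seldom arise. Sitting may be purely historical (Section 9.1), and the three required skills can be met without using the legs. Section 5 reports motor delay in all patients by 12 months and loss of early motor skills in most by age 2. A net loss elsewhere would also prevent response. This stands as a limit on likely size. It does not rule the case out, because no eligibility criterion refers to kicking, and a child has had less time to decline by Week 4 than by Week 48.

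A reader might also infer that the rule was taken from a spinal muscular atrophy trial in which no child would be at the kicking ceiling. Section 14.5 cites that trial to show that "motor milestone assessment using the HINE-2 was feasible and practical in symptomatic, fragile (extremely low functioning at" baseline). It does not say that the responder rule came from there, or what kicking scores those infants had.

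Finally, the endpoint is secondary, no hypothesis is formally tested (Section 14.2), the sample size is not powered (Section 14.1), and listings could show a 4→4 child. All of this is correct, and it keeps the point minor.

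**Conclusion.** The point holds as a wording gap. The maximal-score route for kicking has no baseline condition in Section 14.5 or the synopsis. Applied literally, it makes a 4→4 child a responder when gains and losses in the other six categories are equal, including no change at all. The context suggests that an increase was meant, so the clause is ambiguous, and the error occurs only if it is coded as written.

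The size is at least 10 percentage points per affected child, given at most 10 children in Stage 2. A reader might infer that the responder rate will in fact be inflated by some stated amount. The documents do not support that: they give no baseline HINE-2 distribution, so the number of affected children is unknown and may be zero. Minor severity: a descriptive secondary endpoint, with no alpha or decision threshold attached.

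**What to change.** In Section 14.5 and the synopsis, replace the kicking clause with: *at least a 2-point increase in ability to kick, or an increase from a lower baseline score to the maximal score (touching toes)*. State that the same definition applies when improved categories are counted under condition (ii), and that a child at the maximum at baseline cannot count as improved on kicking.

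This reclassifies only the 4→4 pair; 3→4 still counts as improvement. It costs one clause in two places and a clarifying sentence, with no new data. The downside is that the reported responder rate may be slightly lower.
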